## 6.4. Interim Analyses and Data Monitoring

### 6.4.1. Interim Analysis of Clinical Outcomes

The clinical outcome events adjudicated by independent hepatic outcome committee will be closely monitored in a blinded manner until 100% of the required events have been captured. The projections for the total number of events in three groups (placebo, OCA 10mg, and OCA 25mg) will be generated and reviewed following the Performance Standard Plan. When 288 events in all three groups are expected to be observed based on the modeling projections, it is assumed that the targeted 190 events for 66% IA analysis in two groups (placebo and OCA 25) will have accrued. This will trigger the 66% interim analysis evaluations as presented in [Section 3.2](#).

One interim analysis of the clinical composite outcomes endpoint, including all-cause mortality and liver-related clinical outcomes will be conducted when 66% of the 288 clinical outcomes events are accrued in the placebo and OCA 25 mg groups using the Lan-DeMets O'Brien-Fleming boundaries for efficacy ([Reboussin 2000](#)). Further details on the boundaries and alpha spent in the interim analysis are provided in [Section 3.2](#).

### 6.4.2. Data and Safety Monitoring Committee

An independent DMC will include hepatologists, physicians, epidemiology/cardiology expert(s), and statistician(s) who will not be involved in the study as Investigators, adjudication committee members, or consultants will have oversight over the study conduct as defined by the DMC charter.

The DMC will meet approximately quarterly, and at least every 6 months, at scheduled meetings and ad hoc meetings, as appropriate, to review safety and efficacy data as well as the adjudication assessments from the adjudication committees as specified in the charter. Based on the unblinded review of these data, the DMC will advise the Sponsor on the validity and scientific merit of continuing the study.

Written minutes of both the open and closed DMC sessions will be prepared. The closed minutes will be made available to the appointed Sponsor representatives only after the database is locked.

Data flow, access, process, and disclosure will be described in a DAP and Unblinding Plan.

### **6.4.3. Adjudication Committees**

All suspected liver-related clinical outcomes and major adverse cardiovascular events (MACE) events that occur after administration of the first dose of investigational product will be reviewed by the following blinded adjudication committees, depending on event type, before inclusion in any analysis. The committees and event types they are responsible for adjudicating are as follows:

- Cardiovascular Adjudication Committee: Adjudicates all suspected MACE, including all deaths following the CV Adjudication Charter.
- Hepatic Outcomes Adjudication Committee: The role of the HOC is to review and adjudicate all deaths and suspected liver-related clinical outcomes following the pre-specified criteria described in the HOC Charter.
- Renal Adjudication Committee (RAC) – The role of the RAC is to review potential Acute Kidney Injury (AKI) events and adjudicate an event as AKI following the pre-specified criteria included in the RAC Charter.
- Hepatic safety Adjudication Committee (HSAC) - The role of the HSAC is to review potential hepatic injury triggers to determine whether they meet the pre-specified criteria for hepatic injury as described in the HSAC Charter.

Each adjudication committee will have a charter that documents the reporting of events by the study site, definition of the suspected events to be adjudicated, supply of source documentation to the committee, entire data flow and process from committee membership, review of the events by the committee, reporting of the final assessment, and the working procedures of the committee.

All potential liver-related clinical outcome events, hepatic safety, renal and major cardiovascular adverse events (MACE) will be reviewed by adjudication committees before inclusion in any analysis. The adjudication committee members will be independent hepatologists, nephrologists (cardiologists for MACE) not involved in the study as investigators, DMC members, or consultants. All adjudication committee members will remain blinded to treatment group throughout the study. The data coordinating center will remove all subject identification on the eCRF data and source documentation, as specified in the charter.

#### **6.4.4. Primary Efficacy Analysis**

##### **6.4.4.1. Primary Efficacy Analysis at Month 18**

The primary efficacy analysis at Month 18 will compare OCA to placebo. The primary efficacy analysis will be conducted using the ITT Population.

The primary endpoints for the Month 18 Interim Analysis are:

- Improvement of fibrosis by at least 1 stage with no worsening of NASH (no worsening of hepatocellular ballooning, no worsening of lobular inflammation and no worsening of steatosis)
- Resolution of NASH with no worsening of fibrosis

The primary efficacy analysis at OCA 25 mg dose will test the following hypotheses using the ITT Population:

- H01: The percentage of subjects with fibrosis improvement by 1 stage or more, no worsening of hepatocellular ballooning, no worsening of lobular inflammation, and no worsening of steatosis is equal between placebo and OCA 25 mg groups.
- H11: The percentage of subjects with fibrosis improvement by 1 stage or more, no worsening of hepatocellular ballooning, no worsening of lobular inflammation, and no worsening of steatosis is different between placebo and OCA 25 mg groups.
- H02: The percentage of subjects with NASH resolution and no worsening of fibrosis is equal between placebo and OCA 25 mg groups.
- H12: The percentage of subjects with NASH resolution and no worsening of fibrosis is different between placebo and OCA 25 mg groups.

The primary efficacy analysis at OCA 10 mg dose will test the following hypotheses using the ITT Population:

- H01: The percentage of subjects with fibrosis improvement by 1 stage or more, no worsening of hepatocellular ballooning, no worsening of lobular inflammation, and no worsening of steatosis is equal between placebo and OCA 10 mg groups.
- H11: The percentage of subjects with fibrosis improvement by 1 stage or more, no worsening of hepatocellular ballooning, no worsening of lobular inflammation, and no worsening of steatosis is different between placebo and OCA 10 mg groups.
- H02: The percentage of subjects with NASH resolution and no worsening of fibrosis is equal between placebo and OCA 10 mg groups.
- H12: The percentage of subjects with NASH resolution and no worsening of fibrosis is different between placebo and OCA 10 mg groups.

The primary efficacy analyses at Month 18 will compare placebo and each OCA dose, adjusting for multiplicity as described in [Section 6.3](#) and using a CMH test stratified by the randomization strata (diabetes at enrollment [yes/no] and use of TZDs or vitamin E at baseline [yes/no]).

These analyses, in addition to the sensitivity analyses described in [Section 6.2.3](#), will also be conducted using the mITT, PP, and Full Efficacy Analysis Populations.

#### **6.4.4.2. Primary Efficacy Analysis at End of Study**

The primary efficacy endpoint at the End of Study will be the time to first occurrence of one of the following hepatic adjudicated events (and progression to cirrhosis based on post baseline biopsy including Month 48 biopsy) post-randomization:

- Death (all-cause)
- MELD score  $\geq 15$
- Liver transplant
- Hospitalization (as defined by a stay of 24 hours or greater) for onset of:
  - Variceal bleed
  - Hepatic encephalopathy (as defined by a West Haven score of  $\geq 2$ )
  - Spontaneous bacterial peritonitis (confirmed by diagnostic paracentesis)
- Ascites secondary to cirrhosis and requiring medical intervention (eg, diuretics or paracentesis)
- Histological progression to cirrhosis

The hypotheses testing for the primary efficacy endpoint at the End of Study is:

- H01: The time to first occurrence of any of the hepatic adjudicated events for all-cause mortality and liver-related clinical outcomes are equal between placebo and OCA 25 mg groups.
- H11: The time to first occurrence of any of the hepatic adjudicated events for all-cause mortality and liver-related clinical outcomes are different between placebo and OCA 25 mg groups.
- H02: The time to first occurrence of any of the hepatic adjudicated events for all-cause mortality and liver-related clinical outcomes are equal between placebo and OCA 10 mg groups.
- H12: The time to first occurrence of any of the hepatic adjudicated events for all-cause mortality and liver-related clinical outcomes are different between placebo and OCA 10 mg groups.

The primary efficacy analysis will be conducted using the ITT Population, only including fibrosis stage 2 and 3 subjects. Placebo and each OCA dose will be compared separately using a log rank test stratified by the randomization stratification factor. Kaplan-Meier (KM) estimates of the distribution of the time-to-event will be tabulated and graphed by treatment group. The tabulation will include the KM estimate of the 25th, 50th (median), and 75th percentiles and corresponding 95% confidence intervals (CIs), if the medians can be estimated. The number and percentage of subjects censored and with events will be presented. The hazard ratio and 95% CI

will be estimated using a Cox regression model stratified by randomization strata to estimate the magnitude of the effect.

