### **2.1.2.1. Primary Objective Assessed at End of Study**

- To evaluate the effect of OCA compared to placebo on all-cause mortality and liver-related clinical outcomes as measured by the time from randomization to the first occurrence of any of the following adjudicated events (clinical outcomes composite endpoint):
  - Death (all cause)
  - Model of end stage liver disease (MELD) score  $\geq 15$
  - Liver transplant
  - Hospitalization (as defined by a stay of  $\geq 24$  hours) for onset of:
    - Variceal bleed
    - Hepatic encephalopathy (as defined by a West Haven score of  $\geq 2$ )
    - Spontaneous bacterial peritonitis (confirmed by diagnostic paracentesis)
  - Ascites secondary to cirrhosis and requiring medical intervention (eg, diuretics or paracentesis)
  - Histological progression to cirrhosis

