Approximately 2480 subjects with NASH who meet all eligibility criteria will be randomized to receive OCA 10 mg, OCA 25 mg, or matching placebo in a 1:1:1 ratio for the duration of the study, in conjunction with local standard of care. Randomization of subjects with fibrosis stage 2 or stage 3 will be stratified by presence of diabetes at enrollment [yes/no] and use of thiazolidinediones (TZDs) or vitamin E at baseline [yes/no]. Biopsy-confirmed NASH will be determined by central reading of liver histology at Screening, and all subsequent histology assessments will be performed centrally in a blinded fashion. At Month 18 or early termination, biopsy slides will be paired-read with the screening biopsy in a blinded fashion to minimize temporal bias of the Month 18 biopsy read.

Following Month 18 visits, clinical visits will occur every 6 months for the remaining duration of the study. For any subject who develops an AE of hepatic injury or decompensation, or if cirrhosis is suspected based on criteria other than liver biopsy or clinical outcomes, a liver biopsy is recommended and will be read using Consensus Method except that in a case where a biopsy

was already obtained within 6 months of the suspected liver injury or decompensation event. All deaths and potential liver-related clinical outcomes including clinical events and histological findings of potential disease progression to cirrhosis adjudicated by independent Hepatic Outcome Committee will be used for the End of Study analysis.

[figure not shown]
Investigational product (ie, OCA or placebo) will be taken orally, with water, once daily. Subject safety and laboratory assessments will be evaluated at clinical visits as detailed in the protocol.

With the exception of liver transplant, if a subject experiences a suspected or confirmed clinical outcome event, he or she should continue the regular visit schedule and continue taking investigational product as long as none of the criteria for discontinuation outlined in the protocol have been met. Subjects who discontinue investigational product due to Investigator or Sponsor decision are expected to be followed through to study closure (or at the discretion of the Sponsor).

Details of study procedures and assessments are described in the protocol.

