##### **6.4.7.1. Time to Each Component of the Clinical Outcome Endpoint**

[figure not shown]
[figure not shown]
Time to each of the following components of the clinical outcome endpoint and time to HCC will be analyzed by treatment group using ITT and Full Efficacy Analysis Populations:

[figure not shown]
- Death: date of death
- Liver transplant: date of first liver transplant
- MELD score  $\geq 15$ : date of first occurrence of MELD  $\geq 15$
- Hospitalization (as defined by an inpatient stay of 24 hours or greater) for new onset or recurrence of: variceal bleed, encephalopathy (as defined by a West Haven grade  $\geq 2$ ), spontaneous bacterial peritonitis (confirmed by diagnostic paracentesis): date of earliest hospitalization admission.
- Ascites secondary to cirrhosis and requiring medical intervention: date of earliest ascites start date as an adverse event that required medical intervention.
- Histological progression to cirrhosis: date of biopsy

[figure not shown]
Only adjudicated events (and biopsy confirmed progression to cirrhosis) will be included in the analyses. The time to event of each of the components of the clinical outcome endpoint are defined as follows:

[figure not shown]
- Time to death (all-cause), first MELD score  $\geq 15$  and first liver transplant will be calculated in days as the date of the event minus the date of randomization plus 1. Subjects who do not experience an event will be censored at the date of last contact.
- Time to the first occurrence of onset of ascites (secondary to cirrhosis and requiring medical intervention), will be calculated in days as the first time for onset of the ascites minus the date of randomization plus 1.
- Time from randomization to the date of biopsy confirming histological progression to cirrhosis will be calculated in days as the date of the diagnosis minus the date of randomization plus 1. Subjects who do not experience an event will be censored at the date of last contact.

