- Time to the first occurrence of hospitalization for new onset or recurrence of variceal bleed, encephalopathy, spontaneous bacterial peritonitis will be calculated in days as the first hospitalization admission date/time for new onset or recurrence of the event minus the date of randomization plus 1. The duration between the hospitalization admission date/time and discharge date/time (discharge date/time – admission date/time) must be greater than or equal to 24 hours (1 day). Subjects who do not experience an event will be censored at the date of last contact.

[figure not shown]
KM estimates of the time-to-event will be tabulated and graphed by treatment group. The tabulation will include the KM estimate of the medians and corresponding 95% CIs, if the medians can be estimated. The number and percent of subjects censored and with events will be presented. All summaries of incidence will include the associated exact binomial 95% confidence Interval (CI). Listing of adjudicated events, including progression to cirrhosis will be provided. At the Month 18 Interim Analysis, a listing of adjudicated events will be prepared by DMC vendor without unblinding the Sponsor as described in the DAP.

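### The SAP limits the cirrhosis component of the end-of-study primary composite to histology; the protocol and SAP 2.2.1 do not

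*SAP*

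**What the plan says.** The SAP gives the cirrhosis component in four places. The primary objective (2.1.2.1), the estimand (2.3.2.1) and the primary analysis (6.4.4.2) all list "Histological progression to cirrhosis". The lead-in to 6.4.4.2 ties it to biopsy: "hepatic adjudicated events (and progression to cirrhosis based on post baseline biopsy including Month 48 biopsy) post-randomization". The component analyses in 6.4.7.1 fix the date: "Histological progression to cirrhosis: date of biopsy". They also say "Only adjudicated events (and biopsy confirmed progression to cirrhosis) will be included in the analyses", and for those without an event, "Subjects who do not experience an event will be censored at the date of last contact".

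SAP 2.2.1 reads differently. It states that, for the end-of-study analysis, "clinical events and histological findings of potential disease progression to cirrhosis adjudicated by independent Hepatic Outcome Committee will be used".

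The protocol lists progression to cirrhosis with no histology qualifier in its end-of-study objective (6.4), its assessment table (12) and its primary analysis (16.4.1). Section 16.4.1 admits only adjudicated events and names progression to cirrhosis among them. Section 16.11 sends both clinical events and histological findings of possible progression to the Hepatic Outcomes Committee.

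**The concern.** This component belongs to the only end-of-study primary endpoint, which is tested by a stratified log-rank test with a stratified Cox hazard ratio. Its definition decides who is an event and when. As written, whoever builds the analysis dataset must either restrict cirrhosis to biopsy findings (the four SAP lists) or take every progression that the committee adjudicates (the protocol and SAP 2.2.1). If that choice is made after unblinding, it can be challenged as a post hoc choice of endpoint.

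**Working it through.** No figure in the plan can be reproduced here, so the check is a comparison of texts.

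**1. The definitions side by side**

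| Place | Cirrhosis component |
|---|---|
| SAP 2.1.2.1, 2.3.2.1, 6.4.4.2 | Histological progression |
| SAP 6.4.7.1 | Histological progression, dated at biopsy |
| SAP 2.2.1 | Adjudicated clinical events and histological findings |
| Protocol 6.4, 12, 16.4.1 | Progression, no histology limit |
| Protocol 16.11 | Committee adjudicates clinical and histological evidence |

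Four SAP sections carry the limit. Three protocol sections and SAP 2.2.1 do not.

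**2. Is the protocol wording shorthand for histology?** Protocol Section 12 uses the histological qualifier for the Month 18 endpoint and defines it as fibrosis stage 4 on biopsy. The end-of-study composite in the same section omits the qualifier. The protocol's summary of changes says the broadening was deliberate. That is used here only as evidence of intent; the conflict stands on current text.

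**3. Can progression be recorded without a biopsy?** Protocol 7.4.2 recommends a biopsy, asks for a recorded reason when none is done, and names four findings that may make it unnecessary:

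- ascites, hepatic encephalopathy and variceal hemorrhage, which largely overlap other components (the composite adds conditions such as a hospital stay of at least 24 hours or medical intervention);
- large or red-wale esophageal varices needing treatment, which match no other component.

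So 4 − 3 = 1 finding has no counterpart elsewhere in the composite. Routine biopsy does not close the gap fully. Under protocol 9.9.7, subjects randomized on or after 16 Jul 2017 without a Month 18 biopsy no longer need one unless progression is suspected. Under 8.2.1, some subjects are followed only by telephone or record review.

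**4. One subject traced through both definitions.** Take a subject with treated varices, no bleed, no biopsy and no other component event, whom the committee adjudicates as having progressed.

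- Protocol 16.4.1 and SAP 2.2.1: an event.
- SAP 6.4.4.2 and 6.4.7.1: no event; censored at last contact, as SAP 4 also prescribes.
- Event date: the only rule is the biopsy date in 6.4.7.1, and there is no biopsy.

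**5. Is biopsy progression itself adjudicated?** The parentheticals in 6.4.4.2 and 6.4.7.1 set it beside the adjudicated events. Yet 2.1.2.1 lists it among them, 6.4.3 says that liver outcomes "will be reviewed by adjudication committees before inclusion in any analysis", and 6.4.7.1 ends with "Listing of adjudicated events, including progression to cirrhosis will be provided". This is a lesser wording point.

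**The case against.** The wording difference is not in dispute; its weight is. Five points on the other side deserve an answer.

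- **The charter is unseen.** Confirmation criteria, and perhaps event dates, are in the committee charter, and several SAP sections are missing from the public copy. This stands as a limit. A charter rule would still not tell the analyst which of two SAP statements to follow.
- **The protocol leans towards biopsy.** Section 7.4.2 recommends biopsy so that the case can enter the outcome analysis, and 16.6.1 mentions biopsy-confirmed progression. Both are true, and the protocol does not say outright that a case without biopsy counts. But 16.6.1 gives biopsy-confirmed progression as something included, which excludes nothing.
- **SAP 2.2.1 describes process and does not define an endpoint.** It can be read that way. However, it says the adjudicated findings will be used for the end-of-study analysis, and it names clinical findings as well as histological ones.
- **Section 11 of the SAP proves little.** It lists changes from V1.0 of 24 Jan 2019, before protocol version 11 of 04 May 2021, so the histological wording may simply have been carried over. Agreed: its silence shows only that no departure from the protocol is declared.
- **The subject may not be lost.** A Month 48 or end-of-study biopsy, or a later component event, could still count. That turns a lost event into a late one for some subjects. The protocol also says scheduled biopsies may not be required after a possible outcome event.

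These points bear on size and certainty. They do not reconcile the texts.

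**Conclusion.** The concern holds and should be settled before unblinding. The conflict lies between the current protocol and the current SAP, and within the SAP itself.

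Its size cannot be computed, because the documents do not give the number of cases adjudicated without biopsy. The group is probably narrow. Nothing is claimed about power, event counts or interim timing; SAP 3.1 and 3.2 are not in the public copy.

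The conclusion assumes that the committee can confirm progression without a biopsy. Protocol 16.11 and 7.4.2 allow for this, but only the charter can confirm it. The biopsy-date rule is written for the component analyses; 6.4.4.2 has no separate dating rule for the composite.

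**What to change.** 1. Use one definition in SAP 2.1.2.1, 2.3.2.1, 6.4.4.2 and 6.4.7.1: progression to cirrhosis as adjudicated by the Hepatic Outcomes Committee, in line with the protocol and SAP 2.2.1.
2. Add an event-date rule for progression adjudicated without a biopsy.
3. Report the composite with histology-only progression as a sensitivity analysis, unless SAP 6.2.3 (not in the public copy) already plans it. SAP 2.3.2.2.1 already keeps histological progression as a separate percentage.
4. Reword the parentheticals in 6.4.4.2 and 6.4.7.1 so that biopsy progression is plainly among the adjudicated events.
5. If histology-only is what the sponsor intends, amend the protocol, correct SAP 2.2.1 and state the departure in the SAP.

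Items 1 to 4 cost wording in four SAP sections, one date rule and at most one extra run. No new data are needed, because the committee already adjudicates both kinds of finding. Aligning the biopsy phrase in protocol 16.6.1 is optional tidying. It is a protocol revision subject to ethics review, so it could wait for the next amendment.

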16.4. Efficacy Analyses at End of Study

16.4.1. Primary Efficacy Analysis

All efficacy analysis at EOS will be conducted using the ITT population (only including fibrosis stage 2 and 3 subjects). The hypothesis testing of primary and (key) secondary endpoints will be conducted in with control of Type 1 error (OCA 25 mg, then 10 mg). Adjustments for multiplicity are specified in [Section 16.7](#) and additional details on the testing at EOS will be provided in the SAP.

The primary efficacy endpoint at the EOS will be the time to first occurrence of one of the following post-randomization:

- Death (all-cause)
- MELD score ≥ 15
- Liver transplant
- Hospitalization (as defined by a stay of 24 hours or greater) for onset of:
 - Variceal bleed
 - Hepatic encephalopathy (as defined by a West Haven score of ≥ 2)
 - Spontaneous bacterial peritonitis (confirmed by diagnostic paracentesis)
- Ascites secondary to cirrhosis and requiring medical intervention (eg, diuretics or paracentesis)
- Progression to cirrhosis

The primary efficacy analysis for clinical outcomes at EOS will test the following hypothesis:

- H_{01} : The time to first occurrence of any of the adjudicated events for all-cause mortality and liver-related clinical outcomes are equal between placebo and OCA.
- H_{11} : The time to first occurrence of any of the adjudicated events for all-cause mortality and liver-related clinical outcomes are different between placebo and OCA.

Only adjudicated events (including progression to cirrhosis) will be included in analyses. Placebo and each OCA dose will be compared separately using a log rank test stratified by the randomization stratification factor. Kaplan-Meier (KM) estimates of the distribution of the time-to-event will be tabulated and graphed by treatment group. Subjects without any documentation of events will be censored at the date of last contact. The tabulation will include the KM estimate of the medians and corresponding 95% CIs, if the medians can be estimated. The number and percent of subjects censored and with events will be presented. The hazard ratio and 95% CI will be determined based on a Cox regression model stratified by randomization strata to estimate the magnitude of the effect.

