#### 4. GENERAL STATISTICAL METHODS

Individual subject data obtained from electronic case report forms (eCRFs), local laboratories, central laboratories, external sources, and any derived data will be presented in data listings by subject. All data listings that contain an evaluation date will contain a relative study day. Pre-treatment and on-treatment study days are numbered relative to the day of the first dose of investigational product which is designated as Day 1. The preceding day is Day -1, the day before that is Day -2, etc.

For categorical variables, summary tabulations of the number and percentage of subjects within each category (with a category for missing data) of the parameter will be presented. Percentage calculations will be based on non-missing data unless otherwise specified.

In response analysis [yes/no] of histological endpoints, the comparison between treatment groups will be performed using CMH test stratified by the randomization strata (type 2 diabetes at enrollment [yes/no] and use of TZDs/glitazones or vitamin E at baseline [yes/no]).

For continuous variables, the number of subjects, mean, standard deviation (SD), standard error of the mean (SEM), median, 25th and 75th quartiles, minimum, and maximum values will be presented.

Longitudinal summaries of continuous variables will present absolute values, change, and percentage change from baseline at each post-baseline visit.

For continuous endpoints satisfying normality assumptions, change from baseline and percentage change from baseline over time will be analyzed using mixed-effect repeated measures (MMRM) model with treatment, baseline, visit, visit by treatment interaction and stratification factors to be included in the model. An unstructured covariance model will be used. If the computational algorithm fails to converge, an appropriate covariance structure will be selected. Estimates of least-square (LS) means, standard errors will be presented by treatment group. Unless indicated otherwise 95% CIs will be provided for efficacy endpoints by treatment group.

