### **6.3.2. End of Study Primary Endpoints:**

For the analyses of the clinical outcomes composite endpoint at the End of Study, OCA doses will be compared to placebo in a sequential closed gate-keeping manner using Type I error of 0.03.

- First placebo and OCA 25 mg will be compared with respect to the clinical outcomes composite endpoint. If the comparison achieves statistical significance at the 2-sided alpha level in favor of OCA 25 mg, then
- Placebo and OCA 10 mg will be compared with respect to the clinical outcomes composite endpoint.

The possible scenarios of testing the End of Study, depending on Month 18 Interim Analysis results, are provided in [Table 4](#).

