**Table 4: End of Study Type 1 Error**

Month 18 Interim Analysis				End of Study		
OCA 25 mg		OCA 10 mg		Testing for Clinical Outcomes Endpoint		
Primary Endpoints		Primary Endpoints				
$\alpha$	Achieve Statistical Significance	$\alpha$	Achieve Statistical Significance	$\alpha$ Clinical Outcomes	Both Dose Groups Hierarchal *	Only OCA 10 mg**
0.02	Both	0.02	Both	0.05	OCA 25 mg →10 mg at $\alpha=0.05$	OCA 10 mg at $\alpha=0.05$
			Only one	0.039	OCA 25 mg →10 mg at $\alpha=0.039$	OCA 10 mg at $\alpha=0.039$
	Only one	0.009	Both	0.039	OCA 25 mg →10 mg at $\alpha=0.039$	OCA 10 mg at $\alpha=0.039$
			Only one	0.03405	OCA 25 mg →10 mg at $\alpha=0.03405$	OCA 10 mg at $\alpha=0.03405$

$\alpha$  for Clinical Outcomes endpoint is 0.03 + carried alpha from the Month 18 Interim Analysis depending on the statistical success of primary endpoints at OCA 25 mg and OCA10 mg dose level

\* Following Month 18 Interim Analysis, both OCA arms are continued for Clinical Outcomes.

\*\* Following Month 18 Interim Analysis, only the OCA 10 mg arm is continued for Clinical Outcomes.

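### The primary hazard ratio is reported with a fixed 95% CI although the final test is never made at nominal 0.05, so the interval can exclude 1 when the primary test fails

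*SAP*

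**What the plan says.** **The interval.** SAP 6.4.4.2 compares each OCA dose with placebo by a stratified log-rank test. It then adds "The hazard ratio and 95% CI", which "will be estimated using a Cox regression model stratified by randomization strata to estimate the magnitude of the effect". Protocol 16.4.1 has the matching sentence: "The hazard ratio and 95% CI will be determined based on a Cox regression model stratified by randomization strata". The SAP's general rule points the same way: "Unless indicated otherwise 95% CIs will be provided for efficacy endpoints by treatment group" (SAP Section 4).

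**The test level.** SAP 6.3.2 states that "OCA doses will be compared to placebo in a sequential closed gate-keeping manner using Type I error of 0.03". Protocol 16.7 makes 0.03 a minimum. The footnote to SAP Table 4 explains that alpha "for Clinical Outcomes endpoint is 0.03 + carried alpha from the Month 18 Interim Analysis", and the rows of that table give 0.05, 0.039 or 0.03405 according to the Month 18 results.

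**The interim look.** SAP 6.4.1 plans one interim analysis of the composite, which "will be conducted when 66% of the 288 clinical outcomes events are accrued in the placebo and OCA 25 mg groups", with Lan-DeMets O'Brien-Fleming efficacy boundaries. It refers to SAP Section 3.2 for the boundaries and the alpha spent. Section 3.2 and its Table 2 are not in the text available for this review.

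No available section ties the level of the interval to the level of the test, adjusts the interval for the interim look, or describes the 95% interval as descriptive only.

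**The concern.** The log-rank decision and the hazard ratio with its interval will be printed side by side, and most readers will remember the second. If the interval uses a more lenient level than the test, the two can point in opposite directions: an interval wholly below 1 beside a primary test that did not succeed. Readers would then see apparent proof of benefit that the alpha split between histology and outcomes was designed to withhold. The gatekeeping in SAP 6.3.2 adds to this. OCA 10 mg is tested only if OCA 25 mg succeeds, so a 25 mg interval that excludes 1 could suggest that the gate had opened when it had not.

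**Working it through.** **1. The plan's own figures.** The base alpha is 0.05 − 0.02 = 0.03. For the Truncated Hochberg procedure with gamma 0.1 at alpha 0.02:
- larger p-value: 0.1 × 0.02 + 0.9 × 0.01 = 0.011
- smaller p-value: 0.01
- preserved if only one endpoint succeeds: 0.02 − 0.011 = 0.009

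At alpha 0.009 the larger p-value is compared with 0.1 × 0.009 + 0.9 × 0.0045 = 0.00495, and 0.009 − 0.00495 = 0.00405 is preserved. Hence 0.03 + 0.02 = 0.05, 0.03 + 0.009 = 0.039 and 0.03 + 0.00405 = 0.03405, which are the Table 4 values. The interim count is 0.66 × 288 = 190.08, against the stated 190.

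**2. When the 95% interval excludes 1.** With 288 events and 1:1 allocation (OCA 25 mg against placebo), SE(log HR) ≈ 2/√288 = 0.1179. The 95% interval lies below 1 when HR < exp(−1.960 × 0.1179) = 0.794.

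**3. When the final test succeeds.** The information fraction at the interim is t = 190/288. The SAP names the spending method, but the available text does not say how it is applied to a two-sided alpha, so both common conventions were run:
- alpha/2 spent on each side: 2[1 − Φ(z(1−α/4)/√t)] per side
- one function on the whole two-sided alpha: 2[1 − Φ(z(1−α/2)/√t)]

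The final critical value z solves the bivariate normal equation with correlation √t so that the total error equals alpha. The hazard ratio needed is exp(−z × 0.1179). At alpha 0.03, z is 2.194 (per side) or 2.209 (single function), so HR must be below 0.772 or 0.771.

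First figure per side, second figure single function:

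| Overall alpha | Final nominal p | HR needed | 95% CI excludes 1 but test fails | Matching CI level |
|---|---|---|---|---|
| 0.03 | 0.0283 / 0.0272 | 0.772 / 0.771 | 0.772 (0.771) to 0.794 | 97.17% / 97.28% |
| 0.03405 | 0.0320 / 0.0307 | 0.777 / 0.775 | 0.777 (0.775) to 0.794 | 96.80% / 96.93% |
| 0.039 | 0.0365 / 0.0349 | 0.782 / 0.780 | 0.782 (0.780) to 0.794 | 96.35% / 96.51% |
| 0.05 | 0.0464 / 0.0441 | 0.791 / 0.789 | 0.791 (0.789) to 0.794 | 95.36% / 95.59% |

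The window narrows as alpha is recycled but never closes.

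**4. Example.** An observed HR of 0.78 gives z = −ln(0.78)/0.1179 = 2.108 and p = 0.035. The 95% CI is 0.619 to 0.983. At alpha 0.03 the test fails, since 0.035 exceeds 0.0283. Even a 97% CI, which ignores the interim look, runs from 0.604 to 1.007.

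**5. How often.** The table gives the probability of reaching the final look and landing in the window, so stopping at the interim is allowed for. The true hazard ratios are assumptions.

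| Overall alpha | True HR 0.80 | True HR 0.75 | True HR 0.70 |
|---|---|---|---|
| 0.03 | 8.9% / 9.3% | 8.4% / 8.8% | 5.7% / 6.1% |
| 0.039 | 5.0% / 5.5% | 4.6% / 5.1% | 3.0% / 3.4% |
| 0.05 | 1.2% / 1.9% | 1.1% / 1.7% | 0.7% / 1.1% |

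With no true effect and alpha 0.03 the probability is about 1.1%.

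**6. At the interim.** With 190 events the 95% interval excludes 1 below exp(−1.960 × 2/√190) = 0.752. At alpha 0.03 the boundary is 0.668 (per side) or 0.679 (single function). A contradiction arises there only if an estimate that has not crossed the boundary is reported.

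**The case against.** The strongest reply is that the interval is not the decision rule. SAP 6.4.4.2 gives the Cox estimate the task of describing the size of the effect; success is judged by the log-rank test against the alpha hierarchy and the group sequential boundaries. A uniform 95% level, set as the default in SAP Section 4, is an accepted reporting convention. This stands as far as error control goes. A reader might infer that the 95% interval inflates the type I error, or that the trial could be declared positive on it. The documents do not support either reading, because no section uses the interval to declare success.

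A second reply is that 0.03 is only the floor. This also stands. A reader might take the size at 0.03 as the size in general, but every row printed in Table 4 is higher, and at 0.05 the window is only a few thousandths wide in hazard ratio. The available text does not say which level applies.

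A third reply is that SAP Section 3.2, which holds the boundaries, may print the hazard ratio needed for success or a rule for the interval. That cannot be excluded, although SAP 6.4.4.2 does not point to any such rule. It also means that interval levels derived here should not be written into the plan: the two spending conventions give 97.17% and 97.28% at the final look, and 99.45% and 99.24% at the interim, for the same alpha of 0.03.

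What remains is that the 95% interval is neither matched to the test nor labelled descriptive in the sections that define the primary analysis.

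**Conclusion.** The mismatch is real and is one of reporting. At any alpha the plan allows, the final nominal level is below 0.05 (at most about 0.046), so the 95% interval can exclude 1 beside a failed primary test. At alpha 0.03 this occurs for an observed HR of about 0.772 to 0.794, with a chance of about 8 to 9% at a true HR of 0.75 to 0.80. The chance is about 5% at alpha 0.039 and about 1 to 2% at alpha 0.05.

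These sizes rest on boundaries re-derived from the method named in SAP 6.4.1, on the approximation SE = 2/√events, on 288 and 190 events, and on assumed true hazard ratios. The log-rank test and the Cox interval can also differ slightly. A reader might conclude that the confirmatory result is invalid until this is changed. The documents do not support that, since the decision and its error rate do not depend on the interval. The correction is moderate, not mandatory.

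**What to change.** In SAP 6.4.4.2 and Protocol 16.4.1, state that the hazard ratio for each dose formally tested is reported with a confidence interval at 100 × (1 − nominal two-sided alpha of the look at which the test is made). Take that alpha from the boundaries in SAP Section 3.2 and Table 2 and from the Table 4 row that applies, not from a fixed percentage. If alpha is 0.03, the level at the final look will be about 97.2%. Apply the same rule if the result is declared at the 66% look, and to OCA 10 mg at its own tested level. Keep the 95% interval, if wanted, as a figure labelled descriptive and not for inference.

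The cost is one sentence in each document and a slightly wider headline interval. On the log scale the final interval widens by about 12% at alpha 0.03 (2.194/1.960 = 1.119) and by about 2% at alpha 0.05 (1.992/1.960 = 1.016), with alpha/2 spent on each side. No test, boundary or event count changes.
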